#### 12C. Dose Limiting Toxicity/Adverse Drug Toxicity

#### 12C1. Dose limiting toxicity for Phase I/IIa anakinra study

Dose Limiting Toxicity (DLT) will be defined as any of the following at the 2 or 6 week time point:

- Serious infection qualifying as an SAE (see Section 12) and requiring intervention
- A decrease in the white blood cell count (WBC) to <1500/mm^3 (Grade 3 severity by NIH/NIAID) (NIH 2009)
- An anaphylactoid reaction to an injection of anakinra

A low absolute neutrophil count (ANC) is considered part of the natural course of KD and usually occurs 2 weeks after the initial illness ([name] 2011). Given this, a low ANC will not be considered a DLT or an adverse event in this study.

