#### 11G. Echocardiography Core Lab for Phase I/IIa anakinra study and Combination therapy pilot study

An echocardiogram will be performed at the following time points:

- During initial hospitalization (as soon after admission as possible)
- 48 hours after enrollment in this study
- Study week 2 (Study day 14 ± 7 days)
- Study week 6 (Study day 42 ± 7 days)

2-D transthoracic echocardiograms (2-D Echo) will be performed on all KD subjects according to a strict pre-determined protocol at standard of care time points. All echocardiographic images will be analyzed by [name], Director of Non-Invasive Cardiovascular Imaging at Rady Children's Hospital San Diego. She will be blinded to patient data and clinical status. [name] will also assure adherence to the echo protocols across all echocardiogram technicians. 2-D Echo will be performed at KD diagnosis (within 24h of IVIG infusion) and again at two and six weeks following enrollment with sedation when clinically indicated. The internal lumen diameters of the left main (LMCA), proximal and distal LAD, circumflex, posterior descending, and proximal and distal RCA will each be measured. Dimensions of the LMCA, proximal LAD, and proximal RCA will be adjusted for body surface area and expressed in standard deviation units (Z-scores) (Manlhiot 2009). A variable "Z worst any vessel" will be created to capture the maximal Z score of the RCA or LAD at any time point, as well as the Z-score of the LMCA if an aneurysm is present there with a Z-score larger than that of the RCA or LAD. Coronary artery aneurysm will be defined as a Z-score of 2.5 or larger of the RCA or LAD(Nishiike 2006).

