#### 12B. Duration of Study Drug

#### 12B1. Duration of study drug for Phase I/IIa anakinra study

All subjects will receive 2 weeks of therapy. Subjects with an echo at 2 weeks that shows either a LAD or RCA z-score  $\geq$  2.0 will receive an additional 4 weeks of therapy to complete a total course of 6 weeks. All subjects will remain on study for the full 6 weeks whether or not they are receiving anakinra.

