#### 12C2. Adverse Drug Toxicity for Combination therapy pilot study

An adverse drug toxicity will be defined as any of the following at the 2 or 6 week time point:

- Serious infection qualifying as an SAE (see Section 13) and requiring intervention
- A decrease in the white blood cell count (WBC) to <1500/mm^3 (Grade 3 severity by NIH/NIAID) (NIH 2009)
- An anaphylactoid reaction to an injection of anakinra
- ALT or AST more than 3x the upper limit of age and sex-adjusted normal AND >50% increase over baseline (pre-IVIG)
- CK elevation > 10 times the upper limit of normal or symptoms of muscle pain due to myositis
- A decrease in total cholesterol (TC) level that is at least 10% lower than entry level AND below 100 mg/dl (~2.5th percentile for children age 2 yrs.)

A low absolute neutrophil count (ANC) is considered part of the natural course of KD and usually occurs 2 weeks after the initial illness ([name] 2011). Given this, a low ANC will not be considered an adverse drug toxicity or an adverse event in this study.

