### 12E. Maximum Tolerated Dose for Phase I/IIa anakinra study

The Maximum Tolerated Dose (MTD) will be defined as the highest dose of anakinra studied at which no more than one in six patients experiences a DLT during the 6 weeks of treatment. Subjects will be enrolled at the maximum tolerated dose until a total of 30 subjects have been enrolled in the study. Given the 3+3 design of the study, if there is a DLT then a total of 6 subjects will enrolled per dose level. If we reach the 8 mg/kg/day dose level, then up to a maximum of 12 subjects will be enrolled at a dose level below the MTD (4 mg/kg and 6 mg/kg). This leaves 18 subjects treated at the MTD if the third dosing level is reached. If there are no DLTs at the first two levels, then 3 subjects will be enrolled at the MTD. Thus, between 18 and 24 subjects will be enrolled at the MTD if the 3rd dose level is reached.

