### 12F. Stopping Rules

#### 12F1. Stopping rules for Phase I/IIa anakinra study

**Individual stopping rule:** A subject who experiences a DLT will discontinue anakinra immediately and will be monitored for resolution of the toxicity as medically appropriate. All subjects will be monitored for the 6 weeks from the time of enrollment or until resolution of the DLT, whichever is later.

**Study stopping rule:** Table 6 shows the Phase I dose escalation rules. The study will be discontinued if at the first dose (4 mg/kg/day), the number of subjects that experiences a DLT is greater than 2. Otherwise, the study will determine its MTD using the escalation rules described.

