# 12F2. Stopping rules for Combination therapy pilot study Individual stopping rules:

A subject who experiences any of the following adverse drug toxicities will discontinue anakinra immediately:

- Serious infection qualifying as an SAE (see Section 13) and requiring intervention
- A decrease in the white blood cell count (WBC) to <1500/mm^3 (Grade 3 severity by NIH/NIAID) (NIH 2009)
- An anaphylactoid reaction to an injection of anakinra

A subject who experiences any of the following adverse drug toxicities will discontinue atorvastatin immediately:

- ALT or AST more than 3x the upper limit of age and sex-adjusted normal AND >50% increase over baseline (pre-IVIG)
- CK elevation > 10 times the upper limit of normal or symptoms of muscle pain due to myositis
- A decrease in total cholesterol (TC) level that is at least 10% lower than entry level AND below 100 mg/dl (~2.5th percentile for children age 2 yrs.)

Any subject who experiences an adverse drug toxicity that warrants discontinuation of a study drug will be monitored for resolution of the toxicity as medically appropriate. All subjects will be monitored for 6 weeks from the time of enrollment or until resolution of the adverse drug toxicity, whichever is later.

**Study stopping rule:** The study will be discontinued if three subjects experience adverse drug toxicities.

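### Sections 12C1 and 12C2 count toxicity only at the week-2 or week-6 time point, which as written omits between-visit events and 48-hour labs and contradicts the MTD definition in 12E

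*Combined protocol and SAP*

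**What the plan says.** Section 12C1 (Phase I/IIa) states that a DLT "will be defined as any of the following at the 2 or 6 week time point". The list that follows is a serious infection that qualifies as an SAE and needs intervention, a WBC below 1500/mm³, and an anaphylactoid reaction to an anakinra injection. Section 12C2 (combination pilot) opens the same way, "An adverse drug toxicity will be defined as any of the following at the 2 or 6 week time point", and adds criteria for liver enzymes, CK or myositis, and total cholesterol.

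Section 12E defines the MTD as the highest dose at which no more than one patient in six "experiences a DLT during the 6 weeks of treatment". Under 12B1 some subjects receive only two weeks of drug, but "All subjects will remain on study for the full 6 weeks whether or not they are receiving anakinra".

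The stopping rules reuse these terms. Section 12F1 says "A subject who experiences a DLT will discontinue anakinra immediately". Section 12F2 says "A subject who experiences any of the following adverse drug toxicities will discontinue anakinra immediately", has a parallel sentence for atorvastatin, repeats the six criteria without a time point, and then says "The study will be discontinued if three subjects experience adverse drug toxicities".

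**The concern.** The time qualifier governs every item on both lists, including two that have no natural link to a clinic visit. An anaphylactoid reaction can follow any dose, and a serious infection can start on any day. The laboratory criteria are also measured at 48 hours, which is neither of the two named times. Nothing in the documents says that weeks 2 and 6 are cumulative look-backs or that 48-hour values count.

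The DLT count drives the escalation rules in Table 6 and the MTD. The toxicity count drives the only study stopping rule stated for the pilot, and the pilot's monitoring plan (20B) describes review by the investigators without an outside board. If 12C is followed as written, an early event can drop out of the count that governs the decision. Two careful readers could also classify the same event differently.

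**Working it through.** **The plan's own figure.** Table 7 gives escalation probabilities for the 3+3 rule. With true DLT rate p, the formula described in 12D is (1−p)³ + 3p(1−p)² × (1−p)³. At p = 0.10, 0.15, 0.20, 0.30 and 0.40 it gives 90.6%, 81.4%, 70.9%, 49.4% and 30.9%, against 91%, 81%, 71%, 49% and 31% in the table. Table 7 therefore reproduces. The question is which events count as a DLT, so the rest of the check compares text.

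**The two definitions.** Section 12C1 counts listed events at two time points. Section 12E counts DLTs over six weeks. A WBC below 1500/mm³ at 48 hours that has recovered by week 2 lies within 12E's period but was present at neither time point in 12C1. The same holds for an anaphylactoid reaction on day 3. The two sections therefore give different counts for one rule. Section 12E has a wording problem of its own: it speaks of six weeks of treatment, although 12B1 allows a two-week course.

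**Scheduled post-dose draws** (11D1 and 11D2; total cholesterol is taken to come from the fasting lipid panel):

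| Criterion | Draws after first dose | Share taken at 48 hours |
|---|---|---|
| WBC, Phase I/IIa | 48 h, week 2, week 6 only if on drug | 1 of 3; 1 of 2 if drug stops at week 2 |
| WBC and ALT/AST, pilot | 48 h, week 2, week 6 | 1 of 3 |
| CK and total cholesterol, pilot | 48 h, week 2, week 6 only if on drug | 1 of 3; 1 of 2 if drug stops at week 2 |

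These are counts of draws, not of missed events.

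**Direction.** Every event that meets the literal definition also meets the wider one, so the literal reading can only lower the count. Two hypothetical cases under the plan's own rules show the effect:

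- *Escalation, Table 6.* One subject of three has an anaphylactoid reaction on day 3. The wider reading gives 1 of 3, so the cohort expands to six. The literal reading gives 0 of 3, so there is no expansion on DLT grounds.
- *Pilot stop, 12F2.* Two subjects meet a criterion at week 2 and a third meets one only at 48 hours. The wider reading gives three and the pilot stops. The literal reading gives two and it continues.

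The documents do not say how likely either case is.

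**The case against.** The strongest reply is that the literal reading defeats itself. Parents inject once or twice daily at home, so nobody could mean to restrict injection reactions to a visit day. Weeks 2 and 6 are then the times when DLT status is determined. Section 12D, which asks whether there were DLTs after 2–6 weeks of therapy, fits that view, and so do 12E and the immediate discontinuation in 12F1 and 12F2. This is probably what was intended, but it is not what 12C says, and the 48-hour laboratory values remain ambiguous even under it.

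Three further parts of the reply stand.

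- **12F1 and 12F2 are not further contradictions.** A reader might infer that they conflict with 12C as 12E does. They say what to do once a defined event exists, and they borrow 12C's terms. Leaving out the time phrase points to the wider reading but does not redefine the term.
- **The visit windows do not measure the gap.** A reader might take the ±7-day windows, such as "Study week 6 (Study day 42 ± 7 days" in 11G, and work out what fraction of days goes uncounted. Those windows say when an echocardiogram or research sample may be obtained. No section makes them toxicity-counting windows. On the literal reading one visit inside each window counts, and on the cumulative reading no day is lost.
- **Early events are not lost from safety reporting.** AEs and SAEs are monitored for six weeks, and anaphylaxis and confirmed sepsis are named SAEs. All SAEs go to the anakinra manufacturer within 24 hours. The DSMB evaluates tabulated data before a dose level opens, and the pilot investigators meet after every two subjects.

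It could also be argued that 48-hour values were left out on purpose because acute KD and IVIG disturb them. The plan does not say so for these criteria. Where it sets KD effects aside it does so openly, for ANC and in Table 8, and it omits only ESR at 48 hours on account of IVIG.

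**Conclusion.** The concern holds as a defect of definition. Sections 12C1 and 12C2, followed as written, leave out between-visit events and 48-hour laboratory values, and 12C1 contradicts 12E on the count that sets the MTD. In the pilot, the defined term that feeds the three-subject stop carries the same limit. The only supportable size is the share of scheduled draws shown above. The direction is certain, because the count can only fall.

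A reader might infer that the operating characteristics are materially worse than Table 7 shows, or that past dose decisions were wrong. The documents support neither. Any shift in the escalation or stopping probabilities would need the share of true toxicities that the literal wording captures, and no such figure is given. The 4 and 6 mg/kg cohorts are complete, the Introduction reports no drug-related SAEs, and nothing shows that an early event was excluded. What remains open is the MTD decision at 8 mg/kg and the pilot.

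The conclusion rests on 12C meaning what it says. If the study team already counts cumulatively, the correction records existing practice. It is still worth making, because safety is the primary outcome of both studies.

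**What to change.** - **12C1 and 12C2:** replace the time phrase with *at any time from first dose through the week-6 visit, including 48-hour and unscheduled results*.
- **12E:** say *during the 6-week study period*, which also covers subjects who stop drug at week 2.
- **12F2:** state that the three-subject stop uses the 12C2 definition.
- **Subjects already treated:** check existing AE and laboratory records against the revised definition, and tell the DSMB if any DLT count changes. From Table 5 (3–6 subjects at each of the two completed levels) and the two subjects at 8 mg/kg reported at the August 2017 revision, that was 3 + 3 + 2 = 8 to 6 + 6 + 2 = 14 subjects, plus any enrolled since.

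The cost is wording in four sections and a short record check, with no new visits, samples or subjects. There is a small downside: some early laboratory changes caused by acute KD or IVIG, and some events after drug has stopped, may now be counted. If the sponsor wants any of these excluded, the definition should say so, as it does for ANC.

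One limit remains and should be stated. Subjects who stop at week 2 have no scheduled week-6 WBC (Phase I/IIa) or CK and lipids (pilot). For them those criteria rest on 48-hour, week-2 and any unscheduled values.

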#### 12D. Dose Escalation for the Phase I/IIa anakinra study

The first 3 subjects in the study will be treated with 4 mg/kg/day as an IV dose of 2 mg/kg q 12 h and then as 4 mg/kg/day SQ for 2-6 weeks. If there are no dose limiting toxicities after 2-6 weeks of therapy, the safety and clinical data will be tabulated and presented to the PI, co-investigators and the Data Safety Monitoring Board (DSMB) for evaluation as to opening the next dose level (6 mg/kg) (**Tables 5 and 6**). Additional subjects will be enrolled at the highest dose if a dose limiting toxicity is not reached at 8 mg/kg/day for further study in the Phase IIa (total number of subjects is 30).

Table 6. Dose Escalation Decision Rules				
Subjects with a	Escalation Decision Rule			
DLT at a Given Dose				
0 out of 3	Enter 3 patients at the next dose level until maximum tolerated dose.			
1 out of 3	Enter a total of 6 patients at this dose level.			
	• If 0 of these additional patients experience a DLT, proceed to the			
	next dose level.			
	
 
If 1 of these additional patients experiences a DLT, then dose
 
			
	escalation is stopped (see below)			
≥ 2	At least 3 additional patients will be entered at the next lowest dose			
	level if only 3 patients were treated previously at that dose. This lower			
	dose level will be declared the MTD.			

Probability of Dose Escalation: The following probabilities of dose escalation (**Table 7**) are computed as the sum of the binomial probabilities of the following two possible outcomes that would allow dose escalation to occur: (1) no DLT observed in the first three subjects; or (2) one DLT observed in the first three subjects, followed by no DLT observed in three additional subjects at the same dose level. For example, when the underlying DLT rate is no more than 15%, the probability of dose escalation will be at least 81% or alternatively 19% probability of early study termination. Exact 95% binomial confidence intervals will be used to describe the rate of successful dose escalation.

Table 7: The probabilities for dose escalation in Phase I					
True but unknown DLT rate ≤0.1 ≤0.15 ≤0.2 ≤0.3 ≤0.4					
Probability of escalation	≥91%	≥81%	≥71%	≥49%	≥31%

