# **13. Monitoring Side Effects**

#### 13A. Monitoring side effects for Phase I/IIa anakinra study

Subjects will be monitored for 6 weeks to evaluate for adverse events (AEs). The main side effect of anakinra is an infusion site reaction. The most serious adverse event would be an infection or hypersensitivity reaction. All subjects will be monitored for both AEs and SAEs. An AE is any unfavorable or unintended change in a sign (i.e. abnormal laboratory), symptom or disease temporally associated with the study treatment, whether or not it is considered to be related to the study product.

Table 8: Definition of Adverse Events Associated with Anakinra				
Adverse Event	NOT an Adverse Event (Expected with KD)			
Infusion site reaction	Atopic dermatitis or psoriasis			
Decrease in WBC as per Table 9	Eosinophilia (<35%) or ANC (>500)			
Any infection	Worsening coronary artery dilatation or aneurysm compared to baseline			
	
 
Laboratory values compared to baseline:
 
Worsening anemia
 
Increasing platelet and lymphocyte counts
 
Increasing ESR
 
			

Table 9: Grading Severity of Decrease in WBC Adverse Event (NIH 2009)					
Grade 1 Mild	Grade 2 Moderate	Grade 3 Severe	Grade 4 Potentially Life Threatening		
2,000 – 2,500/mm 	1,500 – 1,999/mm 	1,000 – 1,499/ mm³	< 1,000/mm 		

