#### 13B. Monitoring side effects for Combination therapy pilot study

Subjects will be monitored for 6 weeks to evaluate for AEs. The main side effect of anakinra is an infusion site reaction. The most serious adverse event would be an infection or hypersensitivity reaction. See **Table 8** for definition of AEs associated with anakinra and **Table 9** for grading severity of a decrease in WBC. Subjects will also be monitored for AEs associated with atorvastatin (**Table 10**).

All subjects will be monitored for both AEs and SAEs. An adverse event is any unfavorable or unintended change in a sign (i.e. abnormal laboratory), symptom or disease temporally associated with the study treatment, whether or not it is considered to be related to the study product.

 Table 10: Definition of Adverse Events Associated with Atorvastatin

ALT or AST more than 3x the upper limit of age and sex-adjusted normal AND >50% increase over baseline (pre-IVIG)

CK elevation > 10 times the upper limit of normal or symptoms of muscle pain due to myositis

A decrease in total cholesterol (TC) level that is at least 10% lower than entry level AND below 100 mg/dl (~2.5th percentile for children age 2 yrs.)

A SAE is defined as any event which:

- 1. Is fatal; or
- 2. Is life-threatening (the patient was, in the view of the Principal Investigator, in immediate danger of death from the event as it occurred); or
- 3. Requires hospital admission or prolongs hospitalization; or
- 4. Is persistent or causing significant disability; or
- 5. Required medical intervention, such as major surgery, to prevent a serious outcome; or
- 6. The Clinical Site Principal Investigator considers it to be a serious adverse event.

SAEs for this trial include, but are not limited to, anaphylaxis, arrhythmia, cardiac arrest, cardiogenic shock, death, hearing loss, hepatitis, hypertension, hypotension, myocardial infarction, renal failure, seizures, sepsis (confirmed), or shock.

Any SAE, independent of causality, which occur in a subject in the Trial, assigned to receive Product will be reported to Sobi. Reports shall be sent to the Sobi Drug Safety Department by email ([contact]), or by fax ([contact]), within 24 hours of first awareness. Similar reporting will occur with the FDA and IRBs as stipulated by their reporting rules.

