# **19. Statistical Analyses**

# 19A. Statistical analysis of safety for Phase I/IIa anakinra study and Combination therapy pilot study

Descriptive statistics will be calculated for demographic and baseline characteristics, variables related to biologic activity, immunologic variables, PK variables, and safety data. The study population will be described using summary descriptive statistics such as mean, median, standard deviation, and range for continuous variables and frequencies for categorical variables. All events (AEs, SAEs, and UPRs) will be recorded, documenting the course, outcome, severity, and

relationship to the study treatment. Incidence rates of events and the proportion of subjects prematurely withdrawn from the study due to events will be compiled. Analyses will be performed for all patients who have received at least one dose of study treatment. Deviation from the treatment plan will be recorded in the case report forms. The percentage of subjects failing to complete the study or discontinuing prematurely (as well as the times and reasons for discontinuation) will be reported. Refer to Section 12E for the operating characteristics of the Phase I dose escalation for the Phase I/IIa anakinra study.

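### Sections 12C1 and 12C2 exempt every low ANC from being an adverse event, while Table 8 exempts only ANC above 500, so isolated severe neutropenia is coded two ways

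*Combined protocol and SAP*

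**What the plan says.** Two parts of the protocol set a rule for low neutrophil counts.

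- **Sections 12C1 and 12C2.** Both treat a low ANC as part of the natural course of Kawasaki disease, typically seen about two weeks into the illness. 12C1 concludes that "a low ANC will not be considered a DLT or an adverse event in this study". 12C2 concludes that "a low ANC will not be considered an adverse drug toxicity or an adverse event in this study". Neither gives a floor.
- **Section 13A, Table 8.** The column of findings expected with the disease, and so not adverse events, contains the entry "Eosinophilia (<35%) or ANC (>500" (closing bracket omitted here). No unit is printed. The adverse-event column lists a decrease in total WBC graded by Table 9, but does not name ANC.

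The general definition in Section 13A covers any unfavorable or unintended change "in a sign (i.e. abnormal laboratory), symptom or disease temporally associated with the study treatment", whether or not it is thought to be related to study drug. Section 13B repeats that definition and refers to Table 8 "for definition of AEs associated with anakinra" in the combination pilot.

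Safety is the primary outcome of both studies (Sections 7F1 and 7F2). Section 19A compiles incidence rates of events and states: "Analyses will be performed for all patients who have received at least one dose of study treatment".

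**The concern.** An ANC that falls to 500 or lower fits the general definition in Section 13A and lies outside the Table 8 exemption, so it is an adverse event there. Section 12C says that it is not. Two people coding the same laboratory report could each follow the protocol and disagree.

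At stake is the adverse-event incidence reported for the primary safety outcome. If 12C is followed as written, severe neutropenia with no other finding drops out of that count. Sections 9A and 9B list leukopenia first among the anakinra safety measures, so a reader would expect a severe fall in neutrophils to be visible in the event tables.

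The timing makes such a case plausible. Children enter within 20 days of fever onset and receive at least two weeks of drug, so the period in which 12C expects a low ANC can overlap exposure. Table 8 also expects "Increasing platelet and lymphocyte counts", which can hold the total WBC up while neutrophils fall.

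**Working it through.** The plan gives no figure to reproduce. The check compares the rules case by case and then bounds the effect. The Table 8 limit is taken to be per mm3, the unit used in Table 9.

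**1. Where the rules agree and conflict**

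| Finding | 12C1 / 12C2 | Section 13 with Tables 8 and 9 | Result |
|---|---|---|---|
| Low ANC, above 500 | Not an AE | Not an AE | Agree |
| ANC 500 or lower, total WBC 2,500/mm3 or lower | Low ANC not an AE | AE; the WBC fall also counts under Table 9 | An AE is recorded either way |
| ANC 500 or lower with an infection or SAE | Low ANC not an AE | AE; the infection or SAE also counts | An AE is recorded either way |
| ANC 500 or lower, WBC above 2,500/mm3, no infection or SAE | Not an AE | AE | **Conflict** |

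**2. Is the conflict case possible?** At its edge the neutrophil share is 500/2,500 = 20%, so the gap is a neutrophil share below 20% with ANC at or under 500. With assumed values, WBC 6,000/mm3 and 8% neutrophils give 6,000 × 0.08 = 480/mm3: inside the gap, with no WBC event.

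**3. Effect of one case on incidence.** Section 12D gives the Phase I/IIa size ("total number of subjects is 30") and Section 11A2 a target of 10 for the pilot. All dosed subjects are analysed.

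- Phase I/IIa: 1/30 = 3.3 percentage points
- Combination pilot: 1/10 = 10 percentage points

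The proportion of children with any adverse event moves by this much only if that child has no other adverse event.

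**4. Chance of at least one case.** The documents give no frequency, so the per-child risk p is an assumption. P(at least one) = 1 − (1 − p)^n.

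| Assumed p | n = 30 | n = 10 |
|---|---|---|
| 1% | 26.0% | 9.6% |
| 5% | 78.5% | 40.1% |
| 10% | 95.8% | 65.1% |

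**5. What does not change.** ANC is not among the DLT criteria in 12C1 or the toxicity criteria in 12C2, and Table 8 does not add it. Dose escalation (Table 6), the MTD (12E) and the stopping rules (12F1, 12F2) are the same under either rule.

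**6. Subjects already enrolled.** The 4 and 6 mg/kg cohorts are complete, with at least 3 subjects each (Table 5), and Section 11B1 reports 2 at 8 mg/kg: 3 + 3 + 2 = at least 8.

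**The case against.** The best counter-argument is that the texts can be reconciled. 12C gives the principle, Table 8 is the dedicated adverse-event table and supplies the number, and the specific qualifies the general. Table 8 never lists ANC of 500 or lower as an adverse event; that status is inferred from the general definition and the limit on the exemption. This reading is sensible and is the one the fix adopts. But 12C is unqualified, no section states precedence, and the limit of 500 would have no purpose if every low ANC were exempt.

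A second argument is that little is lost. Sections 9A and 9B name leukopenia, infection and injection site reactions as the anakinra safety measures, and isolated neutropenia is not among them. Event incidence is descriptive, blood counts are collected whatever the coding, and an investigator may still call any event serious. Injection or infusion site reactions are the main expected side effect and count as adverse events, so many children may already have one, and the any-event proportion would not move for them. All of this stands and limits the size of the problem. It does not settle how the event should be coded.

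A third argument is that deleting the limit from Table 8 would restore consistency equally well. It would, but it would leave severe isolated neutropenia out of the event count in studies whose primary outcome is safety. Keeping the limit uses a threshold the protocol already contains.

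**Conclusion.** The inconsistency is real and affects both studies. An isolated ANC of 500 or lower, with total WBC above 2,500/mm3 and no infection or SAE, is an adverse event under Section 13 and not under 12C. The text should be corrected.

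The consequence is confined to adverse-event coding and incidence. It is nil if no case occurs, and otherwise at most 3.3 points per case in Phase I/IIa and 10 points per case in the pilot at the planned sizes. How likely a case is cannot be determined from the documents; the probabilities shown rest wholly on assumed risks of 1% to 10% per child. The mismatch in the text is certain; its practical effect is not.

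**What to change.** Keep the Table 8 threshold and state its unit. Amend 12C1 and 12C2 to say that a low ANC is not a DLT (12C1) or an adverse drug toxicity (12C2), and is not an adverse event while it stays above 500/mm3; an ANC of 500/mm3 or lower is recorded as an adverse event.

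Apply the same rule to Phase I/IIa subjects already enrolled. Tabulate the lowest ANC per subject from the scheduled blood counts, so that the data can be read whatever the coding. State that those counts include a differential, which the eosinophil and lymphocyte entries in Table 8 already presuppose.

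The cost is one sentence in each of two sections, one descriptive table, and a check of existing results for at least 8 subjects. That check is possible only where a differential was recorded, since Section 11D1 lists a white blood count without mentioning one. The reported adverse-event rate may rise slightly, and any reclassified event in a completed cohort may need to be reported. Visits, dosing and sample size do not change.
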